1.0 Research Design

1.1 Purpose/Specific Aims

To test the extent to which tailored outreach text messages that provide a cue to action and an intervention that enhances access to poverty-reducing resources, in combination with a primary care literacy promotion program, can improve parenting behaviors, child language development, and social-emotional skill acquisition among low-income Latino children.

A. Objectives

Aim 1: To test the relative efficacy of 3 literacy promotion interventions on parenting behaviors, child language and social emotional skill acquisition among low-income Latino children

Aim 2: To examine mechanisms underlying the effects of the interventions

Aim 3: To conduct a mixed methods process evaluation of the literacy promotion interventions

Research question (RQ) 1: How are the literacy promotion interventions implemented?

RQ 2: What are barriers, facilitators, and modifications made to the interventions?

RQ 3: What are parents' experiences with the interventions?

B. Hypotheses / Research Question(s)

Hypotheses (H) 1A: Children in the ROR + texts arm will have enhanced language and social-emotional skill acquisition, and parents will describe enhanced parenting behavior, as compared to those receiving ROR only

H1B: Children in the ROR + texts + Connecting NJ (formerly Central Intake) arm will have enhanced language and social-emotional skill acquisition, and parents will describe enhanced parenting behavior, as compared to those receiving ROR only or ROR + texts

H2A: Effects of the interventions on child language and social-emotional outcomes will be partially mediated by the home literacy environment.

H2B: The effect of ROR + texts + Connecting NJ child outcomes will be partially mediated by reduction in parent stress and aspects of positive parenting (responsive verbal interactions)

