- (7) The StimQ-2¹⁸ Infant and Toddler subscales of Parent Verbal Responsivity and Reading, Teaching, Verbal Responsivity, which assess child and parent cognitive home environment, book-reading activities, and parent attentiveness to child language acquisition/skill development. We added 8 questions to the Read Infant version. We also will implement the DialogPR¹⁹, a parent report of shared reading quality, plus an observation of shared reading and free play activities.
- (8) Modified Parenting Your Infant and Parenting Your Toddler surveys, derived from the Parenting Your Child²⁰ measure, to assess the frequency of different parenting/caregiving behaviors and positive parenting/parental warmth. The Parent Discipline Questionnaire, to address negative parenting styles, which includes two questions from the 2000 National Survey of Early Childhood Health²¹ that address disciplining techniques. Our measures for positive and negative parenting behaviors will be comprised from responses to these instruments.
- (9) A modified Parent Reading Belief Inventory (PRBI),²² which measures beliefs and attitudes about reading, reading to one's child, and one's own experiences of reading as a child.
- (10) An adapted version of the Survey of Income and Program Participation,²³ to assess family resource use of community and federal support programs.
- (11) We plan to use a Modified Physician-Parent Communication Survey²⁴ to assess parents' perceptions of clinician's behavior of caring, collaboration, and interest.
- (12) The Parental Stress Scale,²⁵ an adapted version of the Local Inventory of Needs and Knowledge (LINK).²⁶
- (13) We are using a Modified ScreenQ Survey,²⁷ to assess home media environment and child use of cellphones and visual media.

A trained study team member will assist parents in completing all forms. All adapted surveys and questionnaires and ones designed by the team are attached. (“Adapted” surveys are ones to which we made changes or added additional questions; “modified” surveys are ones we limited to components or subscales or otherwise reduced.)

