	(2) Health literacy	Short Assessment of Health Literacy (SAHL)	Enrollment	2.5 minutes
	(3) Discrimination	Discrimination Questionnaire	Enrollment	4 minutes

Process measure	(4) Reach Out and Read Receipt	ROR Receipt Questionnaire	Enrollment, 9 m, 18 m	4 minutes
Primary Outcomes	(5) Language skill acquisition	Expressive One-Word Picture Vocabulary Test - Fourth Edition (EOWPVT-4) Spanish-Bilingual - Complete	18 m	5-20 minutes
		MacArthur Bates CDI	Enrollment, 9 m, 18 m	20 minutes
	(6) Social-emotional skill acquisition	Devereux Early Childhood Assessment (DECA)	Enrollment, 9 m, 18 m	5 minutes
	(7) Shared reading (Parent investment) and parent responsiveness	Modified StimQ Read scale	Enrollment, 9 m, 18 m	5 minutes
		StimQ Parental Verbal Responsiveness	9 m, 18 m	6 minutes
		DialogPR Observation of parent-child interactions	9m, 18 m	4 minutes
	(8) Positive and negative parenting behaviors	Parenting Your Infant, Parenting Your Toddler	Enrollment, 9 m, 18 m	4 minutes
		Parent Discipline Questionnaire	Enrollment, 9 m, 18 m	< 1 minute
Secondary outcomes	(9) Reading attitudes and knowledge	Parent Reading Belief Inventory (PRBI)	9 m, 18 m	3 minutes
	(10) Access to community resources	Adapted Survey of Income and Program Participation (SIPP)	Enrollment, 9 m, 18 m	2 minutes
	(11) Parent-clinician relationship	Modified Physician-Parent Communication Survey	Enrollment, 9 m, 18 m	2 minutes
	(12) Parent stress and wellbeing	Adapted LINK survey	Enrollment, 9 m, 18 m	8 minutes
		Parental Stress Scale	Enrollment, 9 m, 18 m	3 minutes
	(13) Child media use	Modified ScreenQ-I/T 2.0 (Infant/Toddler)	Enrollment, 9 m, 18 m	6 minutes

C. Study Duration

Up to 5 years; participants will be involved up to 2 years.

D. Endpoints

Study participation will conclude upon completion of data collection

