1.4 Preliminary Data

Using community based participatory research methods, we conducted interviews, focus groups, and user testing with 50 low-income, Latino parents and engaged other stakeholders including health professionals, early educators, and community leaders to understand shared reading in the broader context of parenting. The themes we identified aligned with the Health Belief Model, and uncovered targets to enhance ROR. During interviews, low-income, Latino parents identified benefits of shared reading; they viewed it as an important activity that could enhance their children's future. Parents viewed their children as susceptible to language delays and doing poorly in school, citing their own missed educational opportunities; they saw shared reading as an opportunity to avoid these difficulties. These themes align well with the constructs of perceived susceptibility and benefits from the Health Belief Model.

Despite these beliefs, we found a gap between intention and behavior – almost half of the parents we later surveyed (77% Spanish-speaking) reported no shared reading in the last week (79/160) and 85% read ≤ 3 times. Parents intended to engage in shared reading but did not. Once at home other responsibilities (e.g., caring for other children, chores) took their attention away from opportunities for shared reading. One potential reason is that ROR activities are limited to the office, and thus parents do not receive any cues to action in their home environment when needed. Therefore, we designed an

outreach strategy with our stakeholder partners that consisted of text messages to provide a cue to action when parents were at home with their children to overcome this intention to behavior gap. The message content directly addressed beliefs about child development and shared reading that parents reported during interviews and provided reminders and reinforcement. We sought extensive feedback from stakeholders and assessed the acceptability of the messages through focus groups and user testing. We then conducted a RCT comparing the standard ROR to ROR plus texts. We found that ROR plus text improved the home literacy environment compared to ROR only at the 6-month post-assessment. However, while positive; we found the effects of text messages beyond ROR on the home literacy environment and shared reading more specifically are only partial and the effects on child outcomes beyond ROR are not known.

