For the mediation analyses in Aim 2, we will examine the extent to which the home literacy environment mediates the effect of the interventions on language skill and social-emotional skill acquisition using the product of coefficients method with each outcome at each post-intervention timepoint individually.³² We will calculate bootstrap bias-corrected confidence intervals ($n=5,000$) to estimate the proportion of treatment effect explained via the home literacy environment. While we expect the effect of the ROR + text messages (arm 2) intervention will mainly operate through the home literacy environment (parent investment) based on our conceptual framework, we expect that the ROR + text + Connecting NJ (arm 3) intervention will also have effects on parenting stress and other responsive parenting interactions (parental verbal responsiveness) through increased access to poverty-reducing community resources accounting for the greater hypothesized impact. We will test this more complex conceptual framework based on an adaptation of the Gershoff model using Structural Equation modeling without latent factors.

For aim 3, the mixed methods approach will allow us to systematically compare data on intervention implementation with the perspectives of parents and clinicians in an ongoing manner. Integration of quantitative and qualitative data will occur at the design, methods, and reporting levels. We will use a convergent design in which we collect quantitative data on key intervention components in the same time frame as we conduct observation (if possible) of study visits.

Parent-child observations will be analyzed by the study team, led by [name]. The observations will be coded according to parent-child interactive behaviors (did expected behaviors occur or not).

Practice and clinician surveys and clinician interviews will be analyzed using qualitative methods to identify changes and adaptations to ROR implementation protocols over time. The evaluation aims to determine what was implemented, how it was implemented, and what changes occurred to implementation over time. We also seek to understand how clinic context affected implementation. These qualitative findings will help inform our quantitative patient-reported outcomes.

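### Parental Verbal Responsiveness, a listed primary outcome and an H2B mediator, has no enrollment value, and section 6.1 names no baseline covariate to stand in for it

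*Combined protocol and SAP*

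**What the plan says.** Section 1.3 B places PVR under primary outcomes, in the shared reading and parent responsiveness construct, with visits at 9 and 18 months: "StimQ Parental Verbal Responsiveness 9 m, 18 m 6 minutes". Two neighbouring measures are treated differently. The other StimQ scale reads "Modified StimQ Read scale Enrollment, 9 m, 18 m 5 minutes", and the other H2B mediator reads "Parental Stress Scale Enrollment, 9 m, 18 m 3 minutes".

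Section 1.1 B states that the arm 3 effect on child outcomes will be "partially mediated by reduction in parent stress and aspects of positive parenting (responsive verbal interactions"). Section 6.1 carries this into the analysis: arm 3 "will also have effects on parenting stress and other responsive parenting interactions (parental verbal responsiveness"), to be tested in a structural equation model without latent factors.

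Section 6.1 gives two rules for baseline-adjusted outcomes, one for a single post-treatment timepoint and one for several. Both require a baseline assessment. The mediation paragraph uses products of coefficients for the home literacy environment and the structural model for the wider framework. It names no baseline covariate for either.

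The research materials in section 1.3 A list the StimQ-2 "Infant and Toddler subscales of Parent Verbal Responsivity and Reading". No section explains why PVR is left out of enrollment.

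**The concern.** Children enroll at 6 to 12 months, so they are 15 to 21 months old at the first PVR measurement and 24 to 30 months at the second. By then arms 2 and 3 have had 9 or 18 months of intervention, and the parent's starting level of responsiveness is unknown.

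Three things follow:

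- **No analysis rule.** PVR has two post-treatment values and no baseline, so neither adjustment rule in section 6.1 applies to it.
- **Lost precision.** The PVR comparison cannot use its own baseline, and the plan names no substitute.
- **Open mediation path.** Randomization protects the arm-to-PVR path but not the PVR-to-child-outcome path. Parents who were already more responsive may have children with better language in every arm. If earlier parenting is not in the model, that association is credited to PVR and multiplied into the indirect effect. H2B is a stated hypothesis, so one of the trial's aims is affected.

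**Working it through.** **1. The plan's own power figure.** Inputs from section 6.1: difference 0.3 SD, significance level 0.05 (two-sided assumed), 175 completers per arm. Power = Φ(0.3 / (σ√(2/n)) − 1.96). With σ = 1 and n = 175: 0.3 / 0.1069 = 2.806; 2.806 − 1.96 = 0.846; Φ = 80.1%. The stated 80% reproduces. (Completion by exactly 80% of 630 would leave 504, or 168 per arm, and 78.5% power; nothing below depends on this.)

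**2. Precision for PVR.** A covariate with correlation r to follow-up PVR reduces the residual SD to √(1 − r²). The documents do not give r. At 175 per arm and 0.3 SD:

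| r (assumed) | Residual SD | Power |
|---|---|---|
| 0 | 1.000 | 80.1% |
| 0.3 | 0.954 | 83.7% |
| 0.5 | 0.866 | 90.0% |
| 0.7 | 0.714 | 97.6% |

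These are for a single test at 0.05. Section 6.1 applies step-down minP across outcomes and timepoints in the parenting domain, so actual power would be lower. Here r is the correlation of whatever is adjusted for; a proxy such as StimQ Read may well have a smaller r than a true PVR baseline.

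**3. The mediation path.** Let a be the arm effect on PVR, ρ the correlation of baseline with follow-up PVR, and g the effect of baseline PVR on the child outcome, all in SD units. Set the true PVR-to-outcome effect to zero. Regressing the outcome on arm and follow-up PVR then gives a PVR coefficient of g × ρ, and an indirect effect of a × g × ρ instead of zero. None of these inputs is in the documents; assume a = 0.3, ρ = 0.3 to 0.7, g = 0.2 to 0.4.

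- Low end: 0.3 × 0.2 × 0.3 = 0.018 SD.
- High end: 0.3 × 0.4 × 0.7 = 0.084 SD.

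In simulation (175 per arm, 1,500 runs per setting) the PVR path was falsely significant in 21% of runs at the low end and over 99% at the high end. With the true baseline PVR in the model the rate returned to about 5%.

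**4. What a proxy can do.** Suppose the enrollment covariate correlates q with baseline PVR and relates to later PVR and the outcome only through it. The fraction of the bias that remains is (1 − q²) / (1 − ρ²q²). At ρ = 0.5:

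- q = 0.3: 0.91 / 0.9775 = 0.93
- q = 0.5: 0.75 / 0.9375 = 0.80
- q = 0.7: 0.51 / 0.8775 = 0.58

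A single proxy therefore removes part of the bias, and possibly a small part. The documents do not give q.

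**5. Enrollment time.** Summing the table's times for instruments marked Enrollment, with the sub-minute discipline items counted as 1: 12 + 2.5 + 4 + 4 + 20 + 5 + 5 + 4 + 1 + 2 + 2 + 8 + 3 + 6 = 78.5 minutes. Adding PVR gives 78.5 + 6 = 84.5, against a visit of about 90 minutes (section 1.3). Consent takes about 10 minutes (section 4.4 A). If it falls within the visit, the total is 94.5.

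**The case against.** **Timing.** Recruitment was planned for Months 3 to 27 (section 1.5), with a start in autumn 2020, and the current text refers to March 2024 (section 1.3 A). On that timetable enrollment had probably closed before this text was written, although the actual date is not given. A pre-allocation PVR value cannot be collected afterwards. This stands, and it is why the main remedy is an analysis change.

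**Infant form.** Listing Infant subscales does not show that the PVR form suits 6 to 12 months. No StimQ age range is given, and the infant forms of the CDI and DECA run to 18 months, so an infant form could be meant for some children at the 9-month visit. This stands; adding the scale at enrollment must be conditional on its suitability. StimQ Read being given at enrollment is encouraging but not proof.

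**Importance.** Section 6.1 powers the trial on the EOWPVT-4 and DECA, not on PVR. That is correct, and the arm comparisons on those two endpoints are untouched.

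**Reading beliefs.** A reader might extend the point to the reading-belief inventory, also first taken at 9 months ("Parent Reading Belief Inventory (PRBI) 9 m, 18 m 3 minutes") and described in section 1.9 A under a heading for mediators and moderators. Section 1.4 says of the texts: "The message content directly addressed beliefs about child development and shared reading that parents reported during interviews". Beliefs measured under treatment would indeed make a poor moderator. But section 6.1 plans no moderation analysis with this inventory, the schedule lists it as a secondary outcome, and the section 1.4 sentence concerns texts developed for an earlier trial. As an outcome or mediator, 9 months is a reasonable time to measure it. The documents do not support a defect there.

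**Conclusion.** The concern holds in a limited form. PVR has no enrollment value, section 6.1 has no adjustment rule that covers it, and the H2B path from PVR to the child outcome is open to confounding by earlier parenting.

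Two stronger conclusions are not supported. The PVR arm comparison is not biased, because randomization protects it; the loss is precision. Nor can the schedule be said to have clear room for another scale: the margin is 5.5 minutes before consent and gone if consent counts.

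The sizes are illustrative. The power range depends on an unknown correlation and a single unadjusted test. The spurious indirect effect of 0.018 to 0.084 SD depends on assumed a, ρ and g. The direction of the problem does not depend on those exact values: if responsiveness is at all stable and is related to child outcomes from the start, omitting it shifts the indirect effect.

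**What to change.** **Section 6.1, Aim 1.** Add a rule for outcomes without their own baseline. For PVR at 9 and 18 months, adjust for enrollment StimQ Read and enrollment Parenting Your Infant scores.

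**Section 6.1, Aim 2.** In the H2B model, include those two scores, the enrollment Parental Stress Scale, and the baseline child outcome where one exists (CDI, DECA) as covariates in both the mediator and the outcome equations. State in the report that these proxies reduce confounding but do not remove it, and word conclusions about mediation accordingly.

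All of these scores are already scheduled at enrollment, so the cost is a documented change to the analysis plan, best made before outcome data are examined by arm. No participant time is needed.

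**If any dyads remain to be enrolled.** Add the StimQ Infant PVR subscale before allocation, provided the form is suitable at 6 to 12 months. The cost is 6 minutes per parent and an IRB modification. The downside is a longer visit: 84.5 minutes of instruments, excluding about 10 minutes of consent, although section 1.3 A allows the surveys to be scheduled separately from consent. Dyads already enrolled would still rely on the proxy covariates.

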1.4 Preliminary Data

Using community based participatory research methods, we conducted interviews, focus groups, and user testing with 50 low-income, Latino parents and engaged other stakeholders including health professionals, early educators, and community leaders to understand shared reading in the broader context of parenting. The themes we identified aligned with the Health Belief Model, and uncovered targets to enhance ROR. During interviews, low-income, Latino parents identified benefits of shared reading; they viewed it as an important activity that could enhance their children's future. Parents viewed their children as susceptible to language delays and doing poorly in school, citing their own missed educational opportunities; they saw shared reading as an opportunity to avoid these difficulties. These themes align well with the constructs of perceived susceptibility and benefits from the Health Belief Model.

Despite these beliefs, we found a gap between intention and behavior – almost half of the parents we later surveyed (77% Spanish-speaking) reported no shared reading in the last week (79/160) and 85% read ≤ 3 times. Parents intended to engage in shared reading but did not. Once at home other responsibilities (e.g., caring for other children, chores) took their attention away from opportunities for shared reading. One potential reason is that ROR activities are limited to the office, and thus parents do not receive any cues to action in their home environment when needed. Therefore, we designed an

outreach strategy with our stakeholder partners that consisted of text messages to provide a cue to action when parents were at home with their children to overcome this intention to behavior gap. The message content directly addressed beliefs about child development and shared reading that parents reported during interviews and provided reminders and reinforcement. We sought extensive feedback from stakeholders and assessed the acceptability of the messages through focus groups and user testing. We then conducted a RCT comparing the standard ROR to ROR plus texts. We found that ROR plus text improved the home literacy environment compared to ROR only at the 6-month post-assessment. However, while positive; we found the effects of text messages beyond ROR on the home literacy environment and shared reading more specifically are only partial and the effects on child outcomes beyond ROR are not known.

Subsequently, we conducted 21 interviews with Latino parents who received ROR to identify potential mechanisms of action and additional barriers parents encounter. Drivers of ROR's impact included delivery of literacy promotion by a trusted professional and receipt of a children's book. However, parents identified stress associated with material hardship related to poverty as an important barrier to shared reading even when they believed it would be helpful and intended to do it.

1.5 Sample Size Justification

We will recruit 630 Latino parent-child dyads (210 per arm) over a 24-month time period (Months 3-27). This sample size will be sufficient to achieve 80% power to detect a 0.3 standard deviation (SD) difference in language scores between (1) ROR + texts and ROR only and (2) ROR + texts + Connecting NJ and ROR + texts, assuming 20% attrition based on our ongoing work at one of the CHCs. An effect size of 0.3 SD difference would be clinically meaningful since it would be associated with a detectable difference in later cognitive functioning, based on work from a prospective cohort. The proposed sample size will provide 99.9% power to detect a 0.6 SD difference between the community resource arm and ROR only, based on the expected additive effects of the text message and enhanced access to poverty-reducing resources. We will plan for a conservative 24-month recruitment time period to account for seasonal variation in patient volumes and holidays to recruit the target sample (~2-3 participants /site/week).

1.6 Study Variables

A. Independent Variables, Interventions, or Predictor Variables

Participants will be randomly assigned to one of three study arms:

Arm 1 Reach Out and Read: The Reach Out and Read model is a pediatric standard of care and consists of creating literacy rich environments (e.g., children's books present in waiting room), healthcare professionals distributing age and language appropriate children's books, providing anticipatory guidance on shared reading, and modeling dialogical reading which emphasizes responsive and language-rich parent-child interactions.

Arm 2 Reach Out and Read plus text messages: In addition to Reach Out and Read, participants will receive three text messages per week, plus one interactive follow-up message, for the study period with scheduled breaks. Messages will be tailored.

Arm 3 ROR + texts + Connecting NJ: In addition to Reach Out and Read and outreach text messages, and referral to Connecting NJ through electronic referral. Connecting NJ, a program of Central Jersey Family Health Consortium, is based on the national Help Me Grow model and simplifies access to poverty-reducing resources by creating a centralized access point, maintaining an updated data base of resources with existing capacity to support families, and providing case management to ensure families are linked to community resources (e.g., Supplemental Nutrition Assistance Program). They will provide us with data on which community resources participants were referred to.

We will also collect the following process measures:

Table: Quantitative measures of key intervention components and data sources					
Key Component	Arm 1*	Arm 2*	Arm 3*	Process measure	Data source
Literacy rich waiting room	✓	✓	✓	- Availability of children's books - Volunteers in waiting room	ROR parent survey Observation checklist (when and if able to enter clinics)
Children's book distributed	✓	✓	✓	- Family receipt of language appropriate book	ROR parent survey
Anticipatory guidance on shared reading	✓	✓	✓	- Professional discusses reading - Professional models reading	ROR parent survey
Enrollment in text messages		✓	✓	- # of parents requesting stop	Text message portal data
Bidirectional text messages			✓	- # of responses from parents to bidirectional messages	Text message portal data
Parent linked to Connecting NJ			✓	- Electronic referral form	Connecting NJ data
Material support referrals made			✓	- Number & type of referrals	Connecting NJ data
Linkage to services			✓	- Completed referral	Connecting NJ data Parent-reported resources

Arm 1: Reach Out and Read (ROR) only; Arm 2: ROR + texts; Arm 3 ROR + texts + Connecting NJ

B. Dependent Variables or Outcome Measures

- Language acquisition will be assessed using the Expressive One-Word Picture Vocabulary Test - Fourth Edition (EOWPVT-4) Spanish-Bilingual - Complete. This multiple-choice format test consists of 190 items presented in developmental sequence; age-related starting points and cut-off points ensure that only a subset of items is administered.
- MacArthur Bates Communicative Development Inventories (CDIs)¹⁶ are standardized, parent-reported check-lists that assess language and communication in children ages 8-37 months. These checklists focus on children's' nonverbal gestures and early signs of language comprehension, and they are available in English and Spanish.
- Social-emotional skill acquisition will be measured with the Devereux Early Childhood Assessment (DECA),¹⁷ a validated 33-item parent report of socio-emotional problems that is available in both English and Spanish.
- Shared reading and parent responsiveness will be assessed with the StimQ.¹⁸ The StimQ is a parent-reported measure of the cognitive home environment for children that includes domains on shared reading (Reading scale) and responsiveness (Parental Verbal Responsiveness scale). We added 8 questions to supplement this survey. We also will implement the DialogPR¹⁹, a parent report of shared reading quality. We will also conduct observations of parent-child interactions during a shared reading and a play activity to assess parenting strategies around reading. We plan to video- and audio-record these sessions using a video-conferencing software, after consenting the participant to this process. The Research Assistant will observe the parent-child interactions and assess responsiveness and other characteristics of the exchange.

The observations will be done virtually, over the computer or phone, and recorded using a video-conferencing software, so that our study team can: (1) code reading strategies and interactions and (2) have a supervising researcher code the same interactions to strengthen the reliability of the coding.

- Positive and negative parenting behaviors will be assessed through The Parenting Your Infant or Parenting Your Toddler surveys, derived from the Parenting Your Child²⁰ measure. The Parent

Discipline Questionnaire assesses negative parenting disciplining styles and includes two questions from the 2000 National Survey of Early Childhood Health.²¹

